#### 4 Trial Procedures

#### 4.1 Safety Assessments

Safety assessments at virtual visits will be performed as described in the protocol. Assessments which are not currently described for virtual visits will be completed as described below.

#### 4.1.1 Weight and Waist Circumference

Weight and waist circumference will be measured as described in the protocol at the virtual visits defined in this COVID-19 Addendum Schedules of Assessments (Table 1.2-1 and Table 1.2-2) with the following changes:

- Caregivers will be asked to use any weight collection device they currently own regardless of calibration or validation, for weight measurements. (If there is no home weight collection device, the site will provide or reimburse for equipment.);
- Weight and waist circumference measurement does not need to be videotaped. The
  caregiver will be instructed to provide the weight and waist circumference
  measurement result to site staff on the visit day. Subjects will be instructed to be as
  consistent as possible regarding the time of day the measurements are taken, and to
  notify the site staff of the measurement results via telephone, or other means, on the
  appropriate visits.
- Site staff will be instructed to record the weight and waist circumference measurements in eSource, and if there are believed to be any errors, inconsistencies, or safety concerns with the reported home measurement, the medical monitor should be notified.

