#### 3.7.3.3.2 Vital Signs

Vital sign measurements will include body weight (measured at baseline, Week 14, and Week 26), body temperature, systolic blood pressure (SBP), diastolic blood pressure (DBP), and heart rate. The following guidelines will aid in the standardization of body weight measurements:

- The same scale should be used to weigh a given subject each time, if possible.
- Scales should be calibrated and reliable; scales should be at zero just prior to each subject's weigh-in session.

- A subject should void prior to being weighed and be minimally clothed (ie, no shoes or heavy overgarments).
- Weight should be recorded before a subject's meal and at approximately the same time at each visit.

Blood pressure and heart rate measurements will be made in the supine and standing positions after the subject has been in each position for at least 3 minutes. The supine measurements will be performed first, followed by standing. At the in-clinic visits, equipment at the site will be used for the measurements. For the virtual visits, equipment will be provided to the caregiver with instructions for home use. The results of these tests must be reviewed by the investigator in order to determine if any results are considered to be clinically significant.

Subjects should be excluded if they have any vital sign measurement at screening that, in the investigator's judgment, is medically significant in that it would impact the safety of the subject or the interpretation of the trial results. However, any abnormal screening vital sign result(s) considered to be clinically significant may be repeated once to confirm the finding(s) before excluding the subject from the trial. Appendix 1 is included to assist investigators in their assessments of results that may be potentially medically significant, depending on the subject's medical history and clinical presentation.

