8.3 Vital Signs

Vital signs measurements will include body temperature, systolic blood pressure (SBP), diastolic blood pressure (DBP), and heart rate. Blood pressure (ie, SBP, DBP) and heart rate will be measured in the supine and standing positions. Measurements at different positions will be treated as different parameters for purposes of data analysis. Thus, there will be 7 parameters for the vital signs.

The assessment value and the change from baseline value in each of the 7 vital signs parameters during the open-label treatment period will be summarized by visit on the OC data by using descriptive statistics for continuous variables. Likewise, the summary statistics will be computed for the last assessment visit based on the LOCF data.

Potentially clinically relevant vital signs abnormalities during the open-label treatment period will be identified, and the number and percentage of subjects who had such an abnormality in each of the vital signs will be tabulated by prior treatment group based on the observation from the scheduled and the unscheduled (if any) post-baseline visits.

All potentially clinically significant vital signs abnormalities will be listed by prior treatment group, patient ID, baseline value, age, sex, body weight, visit week, type of visit (virtual or in office), and dose at onset of the event if applicable.

Criteria for Identifying Vital Signs of Potential Clinical Relevance for subjects 5 to 17 years of age are provided in Appendix 1.

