8.5.1 Body Weight, Waist Circumference and BMI

Measurements on body weight, waist circumference and height will be collected at two specified visits (ie, Weeks 14 and 26) in office at clinical site during the open-label treatment period. For each visit, BMI will be derived as: weight in kilograms divided by the square of height in meters.

Measurement value and change from baseline value at each of the two specified visits above during the open-label treatment period in each of the above-mentioned four parameters will be summarized on the OC data by using descriptive statistics for continuous variables. Likewise, the summary statistics will also be computed on the LOCF data for the last visit.

Number and percentage of subjects having had significant weight gain (\geq 7% increase in body weight relative to baseline) and significant weight loss (\geq 7% decrease in body weight relative to baseline) during the open-label treatment period will be respectively tabulated by visit and for the overall treatment period as well.

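### Week 14 weights may come from uncalibrated home scales under the COVID-19 addendum, but the SAP treats them as in-office and counts 7% changes without separating them

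*Protocol*

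**What the plan says.** Protocol 3.7.3.3.2 asks for the same scale for a given subject where possible and adds "Scales should be calibrated and reliable". Weight is measured at baseline, Week 14 and Week 26, and in the main schedule (Table 3.7-1) all three are clinic visits.

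The COVID-19 Addendum changes this for Week 14. Its Tables 1.2-1 and 1.2-2 make Week 14 a virtual visit and still mark weight, waist circumference and height. Addendum 4.1.1 asks caregivers to use whatever scale they already own, "regardless of calibration or validation, for weight measurements". If the family has none, "the site will provide or reimburse for equipment". The caregiver reports the result to the site. Where staff suspect an error or inconsistency "with the reported home measurement, the medical monitor should be notified", but no rule says how such a value is analysed.

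SAP 8.5.1 says weight, waist and height "will be collected at two specified visits (ie, Weeks 14 and 26) in office at clinical site". It then tabulates gain and loss of at least 7% by visit and for the whole treatment period, and summarises the last visit on LOCF data. SAP 8.5.2 adds weight, height and BMI z-scores, with counts of subjects whose BMI z-score moves by 0.5 or more. No weight output distinguishes home from clinic readings.

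**The concern.** Protocol 3.5.1 lists the percentage of subjects with clinically significant weight change under the primary endpoint. For a subject on the addendum schedule, the Week 14 change can compare two different devices, one of which need not be calibrated. The SAP describes a measurement setting that does not apply to that subject.

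A threshold count is sensitive to this in a way that a mean is not: random error with no bias can still push subjects across 7%. The overall-period count is exposed because one home reading at Week 14 can make a subject a case even when the Week 26 clinic weight does not. With a single arm, there is no control group in which device error could cancel.

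Addendum 2.5 says any COVID-19 impact on the analyses will be described in the final SAP. The SAP's COVID-19 provisions are a deviation flag (6.3), a discontinuation table (CT-2.1.2) and two AE listings (CT-8.9.1 and CT-8.9.2). None concerns weight.

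**Working it through.** **Which weights are exposed**

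| Time point | Main schedule | Addendum schedules |
|---|---|---|
| Baseline | In office | In office |
| Week 14 | In office | Virtual, so possibly a home scale |
| Week 26/ET | In office | In office |

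A note under Addendum Table 1.2-2 says more loosely that visits after baseline can be virtual or per protocol, but that table's Week 26/ET column is in office. So the Week 26 rows are not exposed. The exposed outputs are the Week 14 rows, the overall-period 7% counts, and last-visit values for a subject whose last weight is a home Week 14 reading.

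**Inputs**

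- From the documents: the 7% threshold (SAP 8.5.1) and at most 119 subjects (SAP 4).
- Assumed, because the documents give none of these: true change at Week 14 with mean 2%, SD 4%; at Week 26 with mean 4%, SD 5%; correlation 0.8; home-scale error SD 1, 2 or 3% of body weight; bias 0 or ±2%; home share at Week 14 of 25% or 100%.

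The plan states no expected incidence, so there is no figure to reproduce.

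**Week 14 alone, all weights at home**

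P(gain ≥ 7%) = 1 − Φ((7 − mean − bias) / √(SD² + error SD²))

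P(loss ≥ 7%) = Φ((−7 − mean − bias) / √(SD² + error SD²))

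| Error SD (bias 0) | Combined SD | Gain ≥ 7% | Loss ≥ 7% |
|---|---|---|---|
| 0 | 4.00 | 10.6% | 1.2% |
| 1% | √17 = 4.12 | 11.3% | 1.5% |
| 2% | √20 = 4.47 | 13.2% | 2.2% |
| 3% | √25 = 5.00 | 15.9% | 3.6% |

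**Direction is not fixed**

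- True mean 7%, SD 5%: gain stays at 50.0% whatever the unbiased error.
- True mean 9%, SD 5%, error SD 3%: gain falls from 65.5% to 63.4%.
- True mean 2%, SD 4%, error SD 2%, scale reading 2% low: gain = 1 − Φ(7/4.47) = 5.9%, below the error-free 10.6%, and loss rises from 1.2% to 5.9%.

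**Overall period (either visit crosses 7%), Week 26 in clinic, by simulation**

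With no device error, gain is 28.7%. With unbiased error:

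| Error SD | 25% of Week 14 at home | All Week 14 at home |
|---|---|---|
| 1% | 28.8% | 29.2% |
| 2% | 29.2% | 30.5% |
| 3% | 29.7% | 32.6% |

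Of 119 subjects, the shift is about 0.1 to 1.2 at a 25% home share and 0.5 to 4.6 at 100%. With error SD 1%, all at home and scales reading 2% low or high, gain is 27.7% or 34.2%.

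**Body weight matters**

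The 7% threshold is 0.07 × 20 = 1.4 kg for a 20 kg child and 0.07 × 50 = 3.5 kg at 50 kg. A 1 kg error is 5.0% and 2.0% of body weight respectively, so the lightest children are the most exposed.

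**The case against.** The strongest reply is that the exposure is narrow. Only one post-baseline weight can be a home reading, and only under the addendum. The Week 26 row, which best reflects long-term change, already rests on clinic weights. At a modest home share the overall count moves by about one subject or less. The trial is descriptive (Protocol 7.4.1), so no test or comparison is affected. Remote assessments arising from COVID-19 are recorded as deviations (Addendum 2.3), and doubtful weights go to the medical monitor. All of this stands and limits the size of the point. It does not make the SAP's in-office statement correct, and nothing links the deviation record to the weight tables.

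A reader might infer that the same defect affects vital signs. The documents do not support that. Protocol 3.7.3.3.2 says "For the virtual visits, equipment will be provided to the caregiver with instructions for home use", so families are not using their own unverified devices. SAP Appendix 1 requires both a criterion value and a minimum change from baseline, and the abnormality listing in SAP 8.3 carries visit type. Added home error could still raise the pooled incidence: for adolescent systolic pressure, an assumed extra SD of 3 to 5 mmHg at six home visits moves it from 11.0% to 13.9-19.1%. That supports at most an optional breakdown. Limiting the main vital-sign table to clinic values would be harmful: it could drop six of nine visits (eight of nine under the addendum) and under-count safety events.

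**Conclusion.** The point holds for weight, at limited size. SAP 8.5.1 misdescribes how Week 14 weight may be collected, and the exposed outputs may be misclassified: the Week 14 and overall-period 7% counts, the Week 14 weight and BMI z-scores, and last-visit values carried from Week 14. For gain the shift is usually upward when mean change is below 7%.

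A reader might infer that the published incidences are inflated. The documents do not show this: bias, error size, home share and true weight change are all unstated, and the sign can reverse. Nor should a large single-visit figure be read as the likely effect. With a true mean of 3%, SD 4% and a 1 kg error in a 25 kg child, gain rises from 16% to 24% (1 − Φ(4/4) to 1 − Φ(4/5.66)). That arithmetic is right, but it applies to Week 14 alone with every weight taken at home.

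On the stated assumptions, the unbiased overall shift runs from 0.1 percentage points (25% at home, error SD 1%) to 3.9 (all at home, error SD 3%). It is worth correcting because the measure is a listed primary safety endpoint and the remedy is cheap.

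**What to change.** In SAP 8.5.1, replace the statement that all Week 14 and Week 26 weights are taken in office. Say that Week 14 weight may be measured at home under the addendum, and that baseline and Week 26/ET are scheduled in office.

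Carry the virtual or in-office visit type, already planned for the vital-sign listing in SAP 8.3, into the weight data. Then present two versions, one with all weights and one with home weights excluded, of:

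- the Week 14 and overall-period counts of gain and loss of at least 7%;
- the weight and BMI z-score summaries, including last-visit values that rest on a home reading.

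Report the number of home weights, so that a reader can judge how much depends on them. Keep all visits in the main vital-sign incidence table; a breakdown by visit type is optional and supportive only.

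The cost is SAP wording and a repeat of existing tables. The home-excluded version will have fewer Week 14 weights. No new data are needed, provided visit type can be linked to the weight record; the SAP currently shows it only for vital signs, so this should be confirmed before database lock.

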#### 4.1.2 Pregnancy

Pregnancy tests will be performed as described in the protocol at the virtual visits defined in this COVID-19 Addendum Schedules of Assessments (Table 1.2-1 and Table 1.2-2) with the following changes:

- For planned visits that require a pregnancy test for females of childbearing potential (FOCBP), the site will provide the necessary tests and instructions so the test may be performed at home;
- Applicable subjects will perform a pregnancy test prior to dosing with IMP, ensuring a date and time-stamped picture or video of the result is taken. The caregiver is to provide/show the result during the virtual visit.
  - If negative, site to inform the subject to proceed with dosing.
  - If positive, the site must instruct the subject to immediately stop taking IMP, and the site will refer to the Pregnancy section of the protocol for appropriate immediately reportable event reporting.

#### 4.1.3 Extrapyramidal Symptom Scales

The Abnormal Involuntary Movement Scale (AIMS) and Barnes Akathisia Rating Scale (BARS) will be assessed at the virtual visits defined in this COVID-19 Addendum Schedules of Assessments (Table 1.2-1 and Table 1.2-2) by providing the subject and caregiver verbal instructions and observing their movements over video. The Simpson Angus Scale (SAS) will not be assessed remotely.

#### 4.2 Efficacy Assessments

Efficacy assessments at virtual visits will be performed as described in the protocol.

## 5 Investigational Medicinal Product

Investigational medicinal product will be shipped directly to caregivers and subjects as per existing procedures for this trial.

# 6 Prohibited Medications (Delayed Rollover Subjects From Trial 331-201-00148)

Delayed rollover subjects must agree to discontinue all prohibited medications during the screening period, after signing the informed consent form/informed assent form, in order to meet the protocol-specified washout periods. Table 6-1 provides the required duration of washout for selected prohibited medications. All other prohibited medications must be discontinued at least 24 hours before the first dose of IMP.

Table 6-1 List of Washout of Prohibited Medications for Delayed Rollover Subjects From Trial 331-201-00148							
Medication	Required Washout Prior to Dosing						
Antipsychotics Oral aripiprazole Oral antipsychotics (other than cariprazine and clozapine) Depot or long-acting injectable antipsychotics or clozapine	14 days 7 days EXCLUDED						
Antidepressants Fluoxetine or Symbyax Monoamine oxidase inhibitors Citalopram and escitalopram Venlafaxine and desvenlafaxine All other antidepressants	28 days 14 days 14 days 14 days 14 days						
Other psychotropics Atomoxetine	For subjects without ADHD diagnosis - 7 days						
Stimulants	Minimum 5× half- life for subjects without diagnosis of ADHD						
Mood stabilizers (ie, lithium or anticonvulsants)  Varenicline	7 days 5 days						
Oral benzodiazepines used as rescue therapy during washout a Lorazepam, oxazepam, diazepam, or clonazepam Other benzodiazepines CYP2D6 inhibitors and CYP3A4 inhibitors and inducers (see Table 4.1-3 of the protocol).	8 hours before scales b 14 days 14 days						

ADHD = attention-deficit/hyperactivity disorder; CYP = cytochrome P450.

<sup>aUse of intramuscular benzodiazepines and continual use of oral benzodiazepines are prohibited throughout the trial. However, limited use of specific oral benzodiazepines is permitted during screening to treat agitation or insomnia as shown in Table 4.1-2 of the protocol.

<sup>bBenzodiazepines must not be administered within 8 hours prior to scheduled efficacy assessments, and EPS scales. Investigators are encouraged to delay scale administration until 8 hours have elapsed, if at all possible. However, if delaying administration of efficacy and EPS scales is not feasible, the scales should still be administered and the use of benzodiazepine documented, including a notation of the drug name, dose, and time of administration in eSource.

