#### 4 Restrictions

#### 4.1 Prohibited Medications

All subjects must agree to abstain from prohibited medications during the trial (Table 4.1-1). Other therapies prohibited prior to enrollment and during the trial are presented in Section 4.2.

Table	e 4.1-1 List of Medications Prohibited During the Trial			
1.	All psychotropic agents including, but not limited to, the following:  a) Antipsychotics, including IR IM and depot or long-acting injectable formulations b) Symbyax c) Antidepressants (including monoamine oxidase inhibitors) d) Mood stabilizers (ie, lithium or anticonvulsants)			
	e) Benzodiazepines, except specific benzodiazepines when used as rescue therapy a f) Stimulants, except when being used for treatment of ADHD. b g) Other psychotropics			
2.	Ramelteon and other non-benzodiazepine sleep aids, except for limited use of specific medications for the treatment of insomnia c			
3.	Antihistamines (except for loratadine and cetirizine)			
4.	Varenicline			
5.	Other nutritional supplements and nonprescription herbal preparations with central nervous system effects (eg, St. John's Wort, omega-3 fatty acids, kava extracts, GABA supplements) unless approved in advance by the medical monitor.			
6.	CYP2D6 inhibitors and CYP3A4 inhibitors and inducers.			
7.	Investigational agents			

GABA = gamma-aminobutyric acid; IM = intramuscular; IR = immediate-release.

<sup>aUse of intramuscular benzodiazepines and continual use of oral benzodiazepines are prohibited throughout the trial. However, limited use of specific oral benzodiazepines is allowed for the control of agitation or insomnia.

<sup>bMust be on a stable dose for ≥ 30 days. Stimulant dose at entry must not be changed during trial participation.

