Informed	X																					
consent/assent																						
Inclusion/exclusion	X	X																				
criteria																						
Medical history	X																					
Psychiatric history	X																					
Verification of stability of comorbid conditions b	X																					
Prior medications and washout, if applicable	X																					
CGI-S	X	X	X	X	X	X	X	X	X	X	X											
SAS, AIMS, & BARS		X		X (AIMS and BARS)				X (AIMS and BARS)			X											
C-SSRS	X	X	X	X	X	X	X	X	X	X	X											
ABC	X	X	X	X	X	X	X	X	X	X	X											
CCI				l								]										

	Screening (Day -28	Screening   26-week Open-label Treatment Period   (Day -28									EOT	Follow- up	
Assessment	to -1)  In office a	Base line (Day 1)	Week 1 (Day 7 ± 2 days)	1 2 (Day 7 ± 2 days) 4 ± 2 days)	3 (Day 2 21 ± 2 s) days)	Week	days)	3 14 ay (Day ± 2 98 ± 2 ys) days)	Week	Week   22   (Day   154 ± 2   days)	Week 26/ ET (Day 182 ± 2 days)	21 (± 2) days after last dose of IMP	Notes
		In office	Virtual								In office		
CCI													
Physical examination	X										X		
Body weight and waist circumference	X	X						X			X		
Height	X							X			X		
Vital signs	X	X	X	X	X	X	X	X	X	X	X		
ECG	X c	X d									X		
Clinical laboratory tests (hematology, serum chemistry, and urinalysis)	X c	X d									X		
HbA1c	X										X		
Prolactin	X										X		
Urine drug screen	X												
Blood alcohol test	X												
Urine pregnancy test	X							X			X		
ACTH	X										X		
Cortisol	X										X		

	Screening (Day -28	26-week Open-label Treatment Period										Follow- up	
Assessment	to -1)	Base line (Day 1)	Week 1 (Day 7 ± 2 days)	Week 2 (Day 14 ± 2 days)	Week 3 (Day 21 ± 2 days)	Week 4 (Day 28 ± 2 days)	Week 8 (Day 56 ± 2 days)	Week 14 (Day 98 ± 2 days)	Week 18 (Day 126 ± 2 days)	Week 22 (Day 154 ± 2 days)	Week 26/ ET (Day 182 ± 2 days)	21 (± 2) days after last dose of IMP	Notes
	office a	office	Virtual	Virtual	Virtual	Virtual	Virtual	Virtual	Virtual	Virtual	office	phone	
TSH with reflex to	X										X		
free T 4 if abnormal													
Coagulation parameters	X										X		
Adverse events	X	X	X	X	X	X	X	X	X	X	X	X	
Concomitant medications	X	X	X	X	X	X	X	X	X	X	X	X	
Dispense IMP		X	X	X	X	X	X	X	X	X			
IMP accountability			X	X	X	X	X	X	X	X	X		

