Note: If efficacy or safety assessments cannot be obtained at consecutive virtual visits, the investigator should discuss possible discontinuation of the subject with the medical monitor.

In order to eligible for this trial, the screening and baseline visits must be in office. All other visits of the open-label treatment period after the baseline visit can be virtual or performed per the protocol.

<sup>aDelayed rollover subjects must agree to discontinue all prohibited medications during the screening period as summarized in Table 6-1.

<sup>bThe investigator should verify the stability of comorbid conditions and that there is no potential new diagnosis since the screening vist in Trial 331-201-00148.

<sup>cThe screening period may be extended in order to repeat clinical laboratory tests and ECGs; if an extension is required, the site should contact the medical monitor.

<sup>dBaseline clinical laboratory tests (hematology, serum chemistry, and urinalysis) and ECGs are not collected if screening clinical laboratory tests/ECGs were obtained within 28 days prior to the baseline visit and within normal ranges.

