7.1 Baseline Definition

An individual subject's baseline value is defined as the observation or assessment taken on the subject at the last visit of the double-blind treatment period in the parent trial. If a subject has separate screening visit(s) after end of the parent trial, then the last observation or assessment prior to the first dose of the open-label IMP will be considered

as baseline. For baseline values, there will be no imputation for missing or unknown values.

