7.4 Medical and Psychiatric History

Medical history and psychiatric history data will be summarized on the Enrolled Sample by prior treatment group using descriptive statistics.

8 Safety Analysis

All safety analyses specified in this section will be performed on the Safety Sample. The baseline of a safety variable is defined as the last observation or assessment in the variable prior to the first dose of the open-label IMP.

Safety is the primary objective for this study. Safety will be assessed by the following standard endpoints for clinical trials and trials of antipsychotic drugs:

- The frequency and severity of treatment-emergent adverse events (TEAEs), serious TEAEs, and discontinuation from trial due to AEs.
- Change from baseline to post-baseline time points in: a) vital sign measurements; b) electrocardiogram (ECG) parameters; c) clinical laboratory tests (including prolactin) and urinalysis; and d) physical examination findings.

- Analysis of potential suicide events recorded on the Columbia-Suicide Severity Rating Scale (C-SSRS).
- Changes from baseline to post-baseline time points in results from extrapyramidal symptoms (EPS) scales (Simpson Angus Scale [SAS], Abnormal Involuntary Movement Scale [AIMS], and Barnes Akathisia Rating Scale [BARS]).
- Percentage of subjects with clinically significant changes in weight (gain or loss) from baseline to specified time points.
- Time to discontinuation.

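### COVID-19 Addendum Table 6-1 excepts cariprazine from the 7-day antipsychotic washout but gives it no rule of its own, so a 24-hour default applies by the letter

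*Protocol*

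**What the plan says.** Protocol section 4.1, Table 4.1-1, prohibits all antipsychotics during the trial. Direct rollovers pass straight from the parent trial's double-blind drug to open-label brexpiprazole. The COVID-19 Addendum adds a second route, for subjects who could not roll over directly or were terminated early because of the pandemic. They have a screening period of Day -28 to -1 and a separate baseline visit. Table 1.2-2 of the Addendum sends sites to one place for the washout: "Delayed rollover subjects must agree to discontinue all prohibited medications during the screening period as summarized in Table 6-1".

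Table 6-1 has three antipsychotic rows:

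- oral aripiprazole, 14 days;
- "Oral antipsychotics (other than cariprazine and clozapine"), 7 days;
- "Depot or long-acting injectable antipsychotics or clozapine", marked excluded.

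The table covers selected medications only. For the rest, the text of Addendum section 6 states: "All other prohibited medications must be discontinued at least 24 hours before the first dose of IMP".

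For a subject with separate screening visits, SAP section 7.1 sets the baseline: "then the last observation or assessment prior to the first dose of the open-label IMP will be considered" baseline. SAP section 8 uses the same principle for safety variables: the "baseline of a safety variable is defined as the last observation or assessment in the variable prior to the first dose" of open-label drug.

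**The concern.** An exception makes sense only if the excepted drug is handled elsewhere. Clozapine is; cariprazine is not. The one oral antipsychotic that the authors singled out without assigning it a rule therefore falls to the shortest period available, although the table's scheme asks for 7 or 14 days for every other oral antipsychotic it allows to be washed out.

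A child who stopped cariprazine 24 hours before the first brexpiprazole dose would comply with the Addendum, and no deviation would arise. ABC, CGI-S, SAS, AIMS and BARS are all scheduled at the delayed-rollover baseline visit. That child's reference values for irritability and extrapyramidal symptoms could then be taken about a day after another antipsychotic. Change in the extrapyramidal scales is among the primary safety endpoints (Protocol section 3.5.1).

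**Working it through.** There is no sample-size or power figure to reproduce. The check matches each drug in the antipsychotic block of Table 6-1 to its rule, then looks for any other rule that could reach cariprazine.

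| Drug | Treatment in Table 6-1 | Resulting rule |
|---|---|---|
| Oral aripiprazole | own row | 14 days |
| Other oral antipsychotics | general oral row | 7 days |
| Clozapine | excepted from the oral row, named in the exclusion row | excluded |
| Depot or long-acting injectables | exclusion row | excluded |
| Cariprazine | excepted from the oral row, named in no other row | default, at least 24 hours |

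The block has three labels and three values that pair one to one, so nothing suggests that a row was lost when the text was extracted.

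**Other rules that might apply.**

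- The remaining rows of Table 6-1 cover antidepressants, atomoxetine, stimulants, mood stabilizers, varenicline, benzodiazepines, and CYP inhibitors and inducers. None names cariprazine.
- The CYP row (14 days) points to Protocol Table 4.1-3. That table is a selected list and does not include cariprazine.
- The delayed-rollover exclusion criteria (Addendum Table 3.2-1) do not mention it. Criterion 10 concerns a likely need for prohibited therapy during the trial, and criterion 11 is general investigator judgment. Neither sets a washout.
- The screening entry "Prior medications and washout, if applicable" in Addendum Table 1.2-2 records what was taken and stopped. It sets no duration.
- SAP table CT-4.1.1 tabulates earlier medications. SAP section 8.8 says this is by drug classification, which does not show the time since the last dose.

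**Size of the gap.** The default is 24 hours = 1 day.

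- Against other oral antipsychotics: 7 - 1 = 6 days shorter.
- Against oral aripiprazole: 14 - 1 = 13 days shorter.

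**Share of the sample.** SAP section 4 caps the sample at the parent trial's 119 randomized subjects. One affected child would be at least 1/119 = 0.84% of it. This shows what one child weighs; it does not estimate how many are affected.

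**Room for a longer washout.** Day -28 to -1 is 28 days, so a 14-day washout fits with 28 - 14 = 14 days to spare.

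**The case against.** The strongest reply is that nobody need be harmed. Several conditions must coincide: a COVID-19 delayed rollover, cariprazine taken between the trials, a stop less than 7 days before dosing, and a site that reads an exception to a 7-day rule as permission for 1 day. The protocol's introduction says risperidone and aripiprazole are the only drugs approved for this indication, and both have a washout in Table 6-1. Screening takes place in the office and reviews washout. All of this stands, and it is why the point is minor. It does not supply the missing rule, and the literal reading is the only one the text offers.

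A second reply is that any replacement period is guesswork, because the documents give no half-life for cariprazine. That also stands. Fourteen days is a borrowed figure, the longest oral antipsychotic washout in the table, and the exception may have been meant to signal something longer or an exclusion.

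Two stronger readings are tempting, and the documents do not support them.

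- A reader might infer that immediate-release intramuscular antipsychotics share the defect. Table 4.1-1 prohibits "Antipsychotics, including IR IM and depot or long-acting injectable formulations", and Table 6-1 has no row for the immediate-release form. But that form is not excepted from any row, so nothing shows that a rule went missing. A 24-hour default could be deliberate there, and comparison with the oral rows is not like for like.
- A reader might infer that the gap spoils an otherwise antipsychotic-free baseline or biases the results. The trial has no such baseline. Under Protocol section 3.2 and SAP section 7.1, direct rollovers from the brexpiprazole arm are rated at the end of double-blind treatment and continue without a break, so they are on drug at baseline. Protocol section 7.4.1 plans descriptive statistics only.

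**Conclusion.** The gap is real and minor. As written, cariprazine has a washout of 1 day for delayed rollovers, against 7 days for other oral antipsychotics and 14 days for oral aripiprazole, and this conflicts with the table's own scheme. An incomplete edit is the likeliest explanation, although the documents do not say so. The conclusion rests on reading the 24-hour default literally and on Table 6-1 being complete as extracted.

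The number of children affected is not given and may be zero. The effect on pooled descriptive results is negligible. What remains is the individual child: an explicit rule for changing from one antipsychotic to another, and a baseline that can be interpreted.

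**What to change.** Make one change to Table 6-1, in either form:

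- add cariprazine to the excluded row with clozapine; or
- add a row requiring at least 14 days for oral cariprazine, with the sponsor confirming whether a longer period within the Day -28 to -1 window is needed.

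If delayed rollovers are already enrolled, add one listing of any whose last cariprazine dose fell within 14 days before the first open-label dose, with the date of that dose. The source should be the prior-medication and washout record taken at screening. Protocol section 3.7.4 is framed around medications taken at the time of consent and could miss a drug stopped shortly before.

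The table change alters how subjects are handled, so it needs a short amendment with IRB/IEC approval under Protocol section 13. The price for a rare affected child is a longer wait for treatment, or exclusion. Because the SAP already states 119 randomized parent subjects, few or no delayed rollovers may remain to be screened (an inference). In that case the listing alone is enough. No analysis set or planned table changes.
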